CGE modelling is an established economic analysis tool, including several applications within health (in the UK and beyond) over the last decade for instance where economic impacts are expected to be diffuse;⁷⁴⁻⁷⁸ such as pandemic influenza, anti-microbial resistance and dietary guidelines.⁷⁹ The model proposed here will draw together two developments made in separate projects. First, the core model used thus far for UK-based analysis is a static UK open-economy CGE model.^{75 79} This will be enhanced by development of a recursive dynamic model, where outputs from the current period are used to build the next period, allowing for feedback effects, such as those developed in previous applications, to be incorporated in the model. Second, in a project focused on malaria in sub-Saharan Africa we have produced a fully integrated model combining modules that reflect demographic and epidemiological parameters mathematically with the CGE core model to facilitate automatic and instant feedback effects between these areas.

As it is micro-founded, this building upwards from economic sectors unlike most macro-economic models that deconstruct from the top-down, the model will enable us to disaggregate sectors to a large degree of detail to reflect the core elements of the systems map (see Appendix A), both in terms of sectors and relationships. This will allow us to draw out the impacts of the SDIL across various industrial sectors, households of different SES, and areas of government, especially HM Treasury, and encompass the multiple dynamic feedback effects predicted by the preliminary systems work (Appendix A). The systems map also provides the basis for specifying the impact points in the model. For instance, labour supply will be impacted by changes in health (morbidity and mortality) and changes to industry profits may impact on participation rate within those sectors; health will also be affected by changes in employment, creating a dynamic interaction over time. Similarly, there will be changes in purchases that affect employment, reflected in demand for labour across different sectors, and the feedback effects from this will also be captured. There could be effects on the import and export of goods as inputs (e.g. sugar) and outputs (e.g. SSBs). The multi-sectoral nature of the model will capture these and relationships between them, guided by the systems map.

Other WPs will feed critical information into the CGE model on both demand and supply sides. WP1, looking at the impacts on the food industry, will enable the development of specific impacts around product change; price, diversification and formulation. WP1, looking at the demand response in purchases of SSBs, will also enable fine-tuning of the relevant elasticities contained within the model for price change for SSBs. The health assessments provided in WP2 by PRIMETIME will be embedded within the demographic and epidemiology modules, and drive the

economic-related health impacts of the SDIL. Work on the micro-economic analysis for WP3, as outlined above, will be used to add greater specificity to the main sectoral impacts beyond health, as well as within the health sector itself. This will also enable fine-grained sectoral disaggregation of the health and social care sector. WP4 will provide additional detail concerning likely impacts across sectors and population groups, and also provide the basis for specific counter-factual scenarios, looking at alternative views of possible responses and future developments in policy and response to policy.

Study populations & data sources

As indicated, the micro-economic analysis will draw upon WP2 for health outcomes data, and WP1 for data on price and demand effects for the targeted SSB and related goods (non-levied beverages, confectionary). This will be supplemented with data related to industry and cross-sectoral impact based on responses to qualitative work in WP4 and monitoring and observation of impact to specific organizations reported in annual financial reports, industry press and government statistics. This will enable reporting of ongoing impacts (and initiatives), and be used to populate core nodes within both micro- and macro-economic models.

Both the micro- and macro-economic models will then simulate the UK population and model the health and economic outcomes of the SDIL across the three time periods of the evaluation, such that they can estimate the (additive) effects of the announcement, legislation, introduction and post-introduction phases. Impacts will be estimated through generation of a counterfactual path compared to a baseline trajectory where the SDIL is not introduced, and also compared with different future scenarios for SDIL.

The health impact for both micro- and macro-economic analyses will be based on the PRIMETIME model used in WP2. This is based on an artificial cohort that incorporates children, adolescents and adults and is representative of the UK population in terms of age and sex. This cohort will be built with reference to mid-year population estimates from the Office for National Statistics and the General Register Offices for Scotland and Northern Ireland. Transition matrices that will dictate the progress of the cohort between the states of the model will be parameterised using disease incidence and mortality estimates taken from national mortality statistics, disease registries and linked datasets of HES and mortality.

For the micro-economic analysis this model will be augmented through clear links to cost drivers, for the NHS and wider health service, and beyond (as indicated it is likely that these will be cost savings for the health service), and use standard health service cost (e.g. using programme-budgeting and HES data) supplemented by specific organisation costs from the wider assessment indicated above (corporation financial reports, industry reports and government statistics on aspects such as employment, revenue growth and tax income).

For the macro-economic analysis, PRIMETIME will be translated in to an epidemiological component linked directly to the CGE model through demographic effects, to estimate the economic impact of changes to health status. The direct financial impact of SDIL, to industry, consumers and retail for example, will be gained from the review of wider economic data as indicated above (corporation financial reports, industry reports and government statistics) and these effects combined will then be used to inform model construction, policy scenarios and feedback effects.

The core data for the macro-economic assessment, on which the CGE model is built, is the social accounting matrix (SAM). This is a matrix that represents the balanced income and expenditure flows of a regional, national or global economy aggregated to make them a manageable size for use in a CGE model (the matrix rows represent income to the economy and the columns represent expenditure). We will use the latest available SAM when the model is constructed, and update it as the project continues. A critical part of SAM construction is to aggregate and disaggregate the sectors (from a few to hundreds) that best represent the issue at hand, and this will be informed by the systems map we have produced already (Appendix A). The SAM is complemented by a series of elasticity parameters that govern the relationships between sectors and economic actors. As we have previously specified a model for the UK these are already incorporated in the model, and will be refined through research conducted especially in WP1 (more precise relationship between change in price and demand), but also WP4 (such as industry response) and the micro-economic assessment indicated earlier on wider impacts.

Proposed outcome and impact measures

The micro-economic analysis will produce estimates of the NHS and social care costs and savings accrued from the SDIL over the short-, medium- and long-term. It will also provide information on wider observed and likely economic impacts to other sectors. Health outcomes, expressed as QALYs, will enable cost-effectiveness estimates of the SDIL to be estimated from both health/social care and societal perspective. The macro-economic analysis will indicate economy-wide impacts on macro-economic variables nationally, as well as disaggregated sectoral impacts and population impacts. These broad economic outcome measures will encompass impacts on the economy overall, and specifically on HM Treasury, industry and consumers by SES.

For example:

- Revenue raised by the levy
- Spending on funding for child health promotion in primary schools
- Extent to which the levy is passed on to consumers (i.e. by increases in prices of SSBs)
- Extent to which the costs of the levy to industry are defrayed by industry through price increases across a broader range of products
- Broad macro-level indicators, such as GDP/GNI, inflation, balance-of-payments and employment
- Other sector specific changes in income, profits and costs
- Overall implementation costs, resulting from changes across government, industry and households

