4.2 Existing research

Soft drink excise tax: reformulation, price, purchasing and consumption

The UK SDIL is different from other SSBs taxes: it is an industry levy rather than an excise tax and has three levels. Our formative research has highlighted several pathways (see systems map in Appendix A) through which the levy could reduce sugar and SSB consumption. Existing research primarily only considers one of these pathways (change in price). Previous studies (of excise taxes) have shown that the tax is passed onto the consumer, although not always fully, and that the taxes/price rises are associated with reduced purchases.^{15 16 20} Economic theory and data strongly suggest that price is an important determinant of SSB purchases.²¹ No study has shown excise taxes are associated with reduced consumption (i.e. drinking of SSB) or changes in health (although modelling studies suggest that such taxes may result in important health gains).

However, the government has made it clear that the SDIL is not a tax on consumers and that companies should seek to reformulate and not pass the levy on to consumers.²² Moreover, the tiered nature of the levy, early signs that industry is reformulating in response to the levy,²³ and

our initial scoping work, all suggest that reformulation may be an important industry response (potentially alongside price rises). No studies have quantified the extent of reformulation in response to levies or taxes.

However, members of our team have recently modelled the potential impacts of the SDIL and have found that price increases, reformulation and other activities (e.g. marketing) that result in consumers switching to low sugar alternatives all have considerable scope to improve health (e.g. 144,000 (95% uncertainty interval: 5,100 to 306,700) fewer adults and children with obesity in the UK, 19,000 (6,900 to 32,700) fewer incident cases of diabetes per year, and 269,000 (82,200 to 470,900) fewer decayed, missing, or filled teeth annually).²⁴ However the study, informed by expert opinion, highlighted considerable uncertainty around the nature and magnitude of the industry response.

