We have chosen data sources to enable study of differential intervention effects across population groups. This will allow us to determine, for example, whether any overall beneficial effects on purchasing or consumption mask detrimental effects in some population sub-groups and hence whether the intervention has equitable or inequitable impacts. As far as possible, all relevant analyses will be conducted for the population as a whole as well as by gender, age and SEP to determine if effects vary across these population groups.

Outcome measures

The range of outcome measures included in WP1 reflects the complexity of our systems map, and the most important of the proposed short-term impacts of the SDIL, prioritised with stakeholder involvement. For drinks market diversity, formulation, price, purchases and consumption, our outcome measures will relate to drinks in four categories:

- non levy-eligible drinks (i.e. non-alcoholic drinks with <5g total sugars/100ml and drinks excluded from the levy) – these will be disaggregated into further sub-categories including

- bottled waters; pure fruit juices; and entirely artificially sweetened, 'diet', drinks
- lower level levy-eligible drinks (i.e. non-alcoholic drinks with $5 < g < 8$ total sugars/100ml)
- higher level levy-eligible drinks (i.e. non-alcoholic drinks with $> 8g$ total sugars/100ml)
- alcoholic drinks

The SDIL is focused on reducing sugar in soft drinks via reformulation³⁹ and a tax was recommended in Public Health England's Sugar Reduction review.⁴⁰ As such the primary aim is to reduce consumption of sugar, rather than consumption of soft drinks *per se*.⁴¹ Furthermore, we are not aware of other pragmatic evaluations of soda taxes that have studied total sugar consumption from drinks as an outcome, making this a significant evidence gap. Thus, in terms of purchasing and consumption, within the four drinks categories listed and also in the confectionery category, we will explore both volume of drinks and confectionery purchased/consumed and total sugars in those.

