We will use an in-house, bespoke dataset (developed during our formative work) to assess non-alcoholic drink market diversification, formulation and price. We have developed automated data collection techniques (i.e. 'data scraping') and will use these to collect monthly, time-stamped data on all soft drinks available for purchase from six online UK supermarkets (Tesco, Morrison's, Asda, Sainsbury's, Waitrose and Ocado). Together these supermarkets (online and in-store) represent more than 75% of the UK grocery market.⁴³ The resultant database (FoodDB) contains data on the complete product range of soft drinks from each supermarket in each month.

We will add data from any new online supermarkets that open during the project. Maintenance of FoodDB will be conducted monthly to ensure that the source code that supplies the dataset continues to run appropriately (it also will be necessary to adapt this source code when online supermarkets change their appearance, format or layout).

For each drink we will continue to collect: date of data collection; nutritional content; price; pack size; serving size; whether or not the drink is on promotion; and manufacturer. Complete datasets for all drinks were collected in December 2013 and October 2016. Data from 1281 Tesco drinks were collected from 2011 to 2016 using a combination of live and archived websites, 391 of which have more than three time points at which data was available. Full monthly data on all drinks from all six major online supermarkets is available from October 2016.

Outcome measures

We will have three outcome measures, one related to each of market diversity, formulation and price:

- number of products (e.g. Coca-Cola, not Coca-Cola 500ml bottle) available across six online supermarkets per month (market diversity)
- mean total sugar concentration in g/100ml per month (formulation)
- mean price (not sales-weighted) in £/100ml per month (price)

These will be considered overall and in each of the four drinks categories described above separately.

Study period and sample size

As described above we have some FoodDB data from 2013, with full data available from October 2016. This study will, therefore, include data from October 2016 (6 months after intervention announcement) – April 2020 (2 years after intervention implementation).

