7.2 WP2 – Impacts on medium to long term health outcomes

Study design

To estimate the impacts of the SDIL over longer time horizons, we will simulate a range of outcomes using a proportional multistate life table approach, adapting an existing life table model (PRIMEtime).⁵⁹ The results from WP1 will be used to estimate effect sizes in terms of sugary drink consumption and free sugars from drinks. The PRIMEtime model will then estimate the impact of these changes on health outcomes over the medium term (next 10 years), and long term (>10 years).

Proposed methods

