The health model will use a proportional multi-state life table approach.⁶⁰ It will be parameterised with data on disease incidence and mortality in the UK taken from the Office for National Statistics, linked datasets of HES and death certificates and disease registries. The diseases in the health model will include dental caries, T2DM, cardiovascular diseases, kidney disease and obesity-related cancers (i.e. cancers of the colon, kidney, liver, breast and pancreas). The results of WP1 will determine the change in mean soft drink consumption (ml/day) and the mean sugar concentration of soft drinks (g/ml). Using a method that we have previously developed to estimate the potential impact of the SDIL under different implementation scenarios⁵⁵, we will convert these outputs into measures of ‘equivalised sugar drink intake’. These changes will be translated into changes in body weight using bespoke meta-analyses of the effect of sugar drink consumption on body weight in both adults and children. For an overview of the trial literature on sugar drink consumption and body weight, see Schillinger et al. (2016).⁶¹ Changes in body weight will be translated into the health outcomes by estimating population impact fractions (PIFs), similar to methods used by the Global Burden of Disease project⁶². The PIFs will be based on hazard ratios linking body weight and the health outcomes, which will be drawn from meta-analyses of prospective cohort studies (e.g. Prospective Studies Collaboration, 2009; WCRF/AICR, 2007). For T2DM, we will model the health impact between soft drinks and disease outcome directly using results from prospective cohort studies.^{59 63} For dental caries we will model the impact between sugar consumption and disease outcome using results from a prospective cohort study.⁶⁴ Work has recently been completed to apply disease utility weights to the PRIMEtime model using a comparable study of population-based EQ-5D scores for the US population adapted for the UK by using UK-based time trade-off tariffs.⁶⁵

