For this project, we will further develop the PRIMEtime model in five ways. First, we will build the first part of the model that estimates changes in soft drink risk as a result of the SDIL, based on results drawn from elsewhere in this project. Here, the inputs will be changes in consumption of sugar drinks (from the interrupted time series analysis of the Kantar World Panel dataset) and changes in average sugar levels in sugar drinks (from the interrupted time series analysis of the foodDB dataset), which will provide population-level estimates that can be converted into changes in ‘equivalised sugar drink consumption’.

Second, we will adapt the existing model to incorporate dental caries, using the datasets described above. Third, we will extend the PRIMEtime model to incorporate children and adolescents who are high consumers of soft drinks by using age and sex-specific estimates of soft drink consumption derived from the NDNS. This will require us to make assumptions regarding how overweight and obesity tracks from childhood into adulthood, which will be informed by the literature. We will conduct sensitivity analyses to test how sensitive our results are to these

changes. However, with the exception of T2DM we do not anticipate that these assumptions will have a big influence on the results as the cardiovascular disease and cancer outcomes that are linked to overweight status in the model do not occur until old age, which for children will not occur for many decades when the model results will be heavily discounted.

Fourth, we will explicitly model lag times between changes in soft drink consumption and health outcomes, with reference to models that have explored time lag between dietary change and health.⁶⁶ The assumptions around time lag will be tested in sensitivity analyses. Fifth, we will re-parameterise the model for the whole UK (currently the model is parameterised for England) using data on health statistics from the Office for National Statistics, the General Register Office for Scotland, the Northern Ireland Statistics and Research Agency and UK results from the Global Burden of Disease study.

Study populations & data sources

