The results from the health model will compare health outcomes in the UK in a baseline scenario where the three stages of implementation of the SDIL (see above) are introduced with a counterfactual scenario where the SDIL is not introduced. Sensitivity analyses will explore scenarios when the early stages of the implementation are introduced without the final implementation of the levy. The data sources that will be used to parameterise the model are described above.

Proposed outcome measures

We will model key health outcomes over medium and long term time horizons, simulating a cohort representing children, adolescents and adults in the UK. The model will estimate the change in dental caries, obesity and T2DM (and associated long term health conditions including cardiovascular disease and renal disease) as a result of age and sex specific estimates of soft drink consumption and average sugar levels in soft drinks. Modelling results will be stratified by socioeconomic groups, to provide estimates of the impact of the SDIL on health inequalities.

The PRIMETIME model will produce outcomes over the medium term (up to 10 years) and long term (>10 years), explicitly accounting for time lag between implementation of the three phases of the SDIL, system change and subsequent changes in health. Sensitivity analyses will explore the effect of applying discount rates to future events. We will use a discount rate of 1.5% as recommended by NICE for evaluations of public health interventions (NICE, 2012).

The outcomes will be changes in the following:

- Medium and long term change in prevalence of dental caries, overweight and obesity
- Change in incidence of T2DM over the medium and long term
- Change in incidence of cardiovascular and kidney diseases and cancers in the medium and long term
- Change in years of life lost due to early mortality from any condition
- Change in quality adjusted life years (QALYs) lost or gained.

Data analyses

We will estimate 95% uncertainty intervals around all of the outcomes, based on Monte Carlo analyses that will sample from distributions around each of the model parameters included in the analysis (e.g. the relative risk estimates associated with dietary change and health outcomes; the effect size of the intervention etc.) Since the PRIMETIME model only includes risk parameters that are statistically significant at a 5% level, it follows that the uncertainty associated with the diet-

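### WP2 names its drink exposure inconsistently and takes the sugar level from a product list that has no purchase weights and no announcement effect

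*Protocol*

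**What the plan says.** Section 7.2 of the protocol states the input to the health model four times.

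- **Study design:** WP1 will supply "effect sizes in terms of sugary drink consumption and free sugars from drinks".
- **Proposed methods, description of the health model:** WP1 will determine the "change in mean soft drink consumption (ml/day) and the mean sugar concentration of soft drinks (g/ml"). These are then converted to a single equivalised intake by a method cited but not shown. No data source or weighting is given.
- **Proposed methods, first planned development:** "the inputs will be changes in consumption of sugar drinks (from the interrupted time series analysis of the Kantar World Panel dataset"), together with "changes in average sugar levels in sugar drinks (from the interrupted time series analysis of the foodDB dataset").
- **Proposed outcome measures:** results follow from "age and sex specific estimates of soft drink consumption and average sugar levels in soft drinks".

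Section 7.1 sorts drinks into four categories by sugar content and levy status. The non levy-eligible category is split further into "bottled waters; pure fruit juices; and entirely artificially sweetened, 'diet', drinks". Section 7.2 does not say which categories make up 'soft drinks' or 'sugar drinks'.

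The FoodDB outcome in Study 1a is "mean total sugar concentration in g/100ml per month (formulation"). Study 1a says that FoodDB records products, not purchases. It uses data from October 2016 and fits implementation as the only intervention point. Study 1b uses KWP from April 2014 to March 2020, fits both announcement and implementation, and already lists total sugars in purchased drinks, by category, as an outcome.

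**The concern.** This input carries the levy's effect into modelled obesity, diabetes, QALYs and costs, so its definition changes the estimate. Three things are at stake.

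- **Switching to diet drinks.** Section 4.2 says that price rises, reformulation and other activities that "result in consumers switching to low sugar alternatives all have considerable scope to improve health". Whether switching reaches the model depends on the drink set and on how the mean sugar level is weighted.
- **Reformulation.** A mean over a product list counts a minor product as much as a market leader. Multiplied by a purchase volume, it does not give the sugar in the drinks actually bought.
- **Timing.** Section 7.2 compares all three stages of the levy with no levy, and plans sensitivity scenarios with the early stages only. The named sugar source starts six months after the announcement and estimates no announcement effect.

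**Working it through.** The protocol gives no figure for this input, so there is nothing to reproduce. The conversion method is not shown, so I assume that the exposure is proportional to volume × mean sugar concentration. The drink shares, switching fractions and sugar contents below are assumptions, not document figures.

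**1. Switching to diet drinks.** Let total volume be V, the sugary share s, the sugary concentration c, and diet drinks 0 g/100ml. A fraction f of sugary volume moves to diet drinks, with V and the product range unchanged.

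True change in sugar = V·s·(1−f)·c / (V·s·c) − 1 = −f.

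| Reading of the input | Volume | Concentration | Modelled change |
|---|---|---|---|
| A. Soft drinks including diet, product-list mean | unchanged | unchanged | 0% |
| B. Soft drinks including diet, purchase-weighted mean | unchanged | s·c becomes s·(1−f)·c | −f |
| C. Sugar drinks only, product-list mean | falls by f | unchanged | −f |

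For f = 10% and 25%, A gives 0% both times, while B and C give −10% and −25%. This holds for s from 0.4 to 0.8 and c of 6 or 10 g/100ml, because s and c cancel.

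Numerical example: 100 ml/day sugary at 10 g/100ml plus 100 ml/day diet, with 20 ml switched.
- True sugar: 10 to 8 g/day (−20%).
- A: volume stays at 200 ml and the product mean does not move (0%).
- B: the weighted mean goes from 10/200 to 8/200 g/ml (−20%).
- C: volume goes from 100 to 80 ml (−20%).

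**2. Reformulation weighted by product count.** Take a fixed set in which every drink starts at 10 g/100ml. Drinks making up a share p of products and w of volume go to 4.5 g/100ml. The relative change for each such drink is 4.5/10 − 1 = −0.55.

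- Purchase-weighted change = −0.55·w. With w = 0.5 this is −27.5%.
- Product-list change = −0.55·p. With p = 0.10, 0.25, 0.50 and 0.80 this is −5.5%, −13.75%, −27.5% and −44%.

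The two agree only when p = w. The error can go either way.

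**3. Products leaving the set.** Study 1b assigns drinks to categories from product-specific nutrition data, so a product can change category when reformulated. Suppose 'sugar drinks' means levy-eligible drinks, with 100 ml at 10 g/100ml, half of it reformulated to 4.5.

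- True change: (50×10 + 50×4.5)/(100×10) − 1 = 725/1000 − 1 = −27.5%.
- Modelled: the reformulated half drops out, (50×10)/(100×10) − 1 = −50%.

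**4. Timing.** FoodDB's counterfactual is the trend from October 2016 to implementation. Section 4.1 says that reformulation was already occurring, so any that followed the announcement sits in that baseline. KWP has two years before the announcement and fits both points.

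**The case against.** A reader might infer that the plan, as written, scores switching to diet drinks as zero. The strongest case against that reading is sound. The paragraph that speaks of soft drinks does not say that diet drinks are included, and it names no source and no weighting. FoodDB is named only in the later, more operational paragraph, where it is tied to sugar drinks, and there switching is captured through volume. Reading A therefore joins the drink set of one paragraph to the data source of another. Even with diet drinks included, a purchase-weighted mean recovers the whole change. Section 4.2 also says that the team's earlier modelling of the levy covered switching, and WP2 reuses a method developed for levy scenarios. The documents do not show that method, so they do not support a claim that switching is lost.

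Reading A is still not far-fetched. Study 1a describes FoodDB as holding the full range of soft drinks, and its sugar mean is the only listed WP1 outcome expressed as a concentration.

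A second fair objection concerns the remedy. Replacing the input with sugar from all non-alcoholic drinks would bring in pure fruit juice, and KWP records total, not free, sugars. That stands, and the fix below allows for it.

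The objections do not answer the pairing itself. Even on the reading most favourable to the plan, a purchase volume is combined with a sugar level that has no purchase weights and no announcement effect. Section 7.1 mentions some FoodDB data from before October 2016, but Study 1a does not analyse them.

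**Conclusion.** The point holds in a limited form. Section 7.2 uses three descriptions of one input and defines none of them. Its only sourced version combines KWP purchases with a FoodDB product mean. That rule cannot give the change in sugar of drinks bought unless product share and volume share coincide, and it cannot supply the announcement effect on sugar level that the staged scenarios need.

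The size depends on the reading. The loss of switching (0% against −10% or −25%) is conditional on diet drinks counting as soft drinks and on the FoodDB mean being used. The overstatement under a levy-eligible set (−50% against −27.5%) is conditional on that definition and on the assumed reformulation. All of these figures are illustrations that treat exposure as volume × concentration. The inconsistency of terms and the mismatch of sources and time periods rest on the text alone. This should be corrected before the first module of the model is built.

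**What to change.** - Define one drink set and use it in every statement of the input in Section 7.2. Fix it so that a product does not leave when its sugar content changes, for example by defining it by type of drink rather than by sugar band. State whether diet drinks are in it. Exclude pure fruit juice or handle it separately.
- Take both volume and sugar from KWP for that set: sugar purchased (kg, already a Study 1b outcome) divided by litres purchased. The concentration is then purchase-weighted and covers both announcement and implementation.
- Keep FoodDB for describing reformulation and for separating it from switching.
- State that KWP total sugars stand in for free sugars. Study 1c already argues that nearly all sugar in drinks other than fruit juice is added, and it already relies on KWP for up-to-date sugar content.

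The cost is a rewording of Section 7.2, one extra derived KWP series and a small change to a module still to be built. No new data source is needed.
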